9.1. Adverse Events

Adverse event terms recorded on the eCRFs will be coded to PTs using version 11.0 or later of the Medical Dictionary for Regulatory Activities (MedDRA). Toxicity grade will be defined according to the version 4.0 or later of the National Cancer Institute (NCI) Common Terminology Criteria for Adverse Events (CTCAE).

A treatment emergent adverse event (TEAE) is defined as any AE with an onset date on or after date of first dose of study product, or any ongoing event on the date of first dose that increases in CTCAE grade after date of first dose. Only TEAEs with an onset date before date of last dose + 28 days will be tabulated in summary tables. Adverse events that begin prior to first dose will be captured in the medical history.

Furthermore each TEAE will be classified based on the period in which it started. Primary period TEAEs will be defined as TEAEs with onset date on or after the date of the first dose of study product and before the date of the second dose of study product. Booster period TEAEs will be defined as TEAEs with onset date on or after the date of the second dose of study product.

For the purpose of calculating treatment emergence, period, and inclusion in summary tables, incomplete onset dates will be imputed as detailed in [Appendix C](#) of this document.

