9.1.1. Incidence of Adverse Events

The frequency and percentage of subjects with TEAEs will be tabulated for overall incidence by system organ class (SOC) and PT for primary period TEAEs, booster period TEAEs and overall.

TEAEs will also be summarized by treatment arm and overall for the highest CTCAE grade and highest relationship to study treatment within each subject. Related TEAEs, serious TEAEs, related serious TEAEs, and TEAEs resulting in study product discontinuation will be similarly summarized. Additionally, the incidence of TEAEs and related TEAEs will be summarized by PT in descending order of total frequency. The incidence of TEAEs coded as injection site reactions will be summarized by type of injection (primary or booster) and by arm.

At each level of summarization, a subject will be counted only once for each AE he/she experiences within that level.

Data listings of all AEs and SAEs will be provided. Adverse events presented in the listings will be those recorded from the first dose date through the end of follow-up.

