The simulation software used to plan the trial requires specification of the number of subjects to be accrued and the period of time over which accrual is to take place (as is usual with trial planning software). These simple specifications would generate an accrual distribution that is uniform, that is, a constant accrual rate. But since it is unrealistic to assume uniform accrual the software also allows specification of an arbitrary accrual distribution through the specification of intervals and accrual in each interval. An additional feature, and the one used in these computations, allows specification of a linear ramp time for the accrual distribution from which the accrual distribution is generated. The linear ramp time must be less than or equal to the total accrual time. Given the linear ramp time the accrual distribution is generated by assuming zero accrual at time zero and a constant accrual rate increase from time zero through the time specified by the linear ramp time, after which the accrual rate is uniform from the linear ramp time until the end of accrual. The rate of accrual increase during the ramp time and the constant accrual rate after the linear ramp time are derived from the total accrual, the total accrual time, and the linear ramp time. For example, for the computations done in this SAP the following specifications were used: total accrual time of 30 months for 1200 patients and with a linear ramp time of 19 months. Given these three specifications it was computed that the accrual distribution (by month) would have 645 subjects to be accrued after month 19 (uniform accrual rate $645/11 = 58.6$ per month for the last 11 months), and that the other 555 subjects were to be accrued in linearly increasing monthly intervals from the start of the trial through month 19 (accrual rate increase of 3.08 per month). This characterization of the approximate accrual distribution was specified as an approximation to the early accrual experience in the ongoing phase 3 trial, and the projections going forward. [Figure 1](#) illustrates this accrual distribution.

Figure 1: Accrual Distribution

16. Appendix C: Imputation Algorithm for Partial and Missing Dates

Adverse Event

If onset date is completely missing, onset date is set to date of first dose.

If year is present and month and day are missing:

If year = year of first dose, then set month and day to month and day of first dose.

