If year < year of first dose, then set month and day to December 31.

If year > year of first dose, then set month and day to January 1.

If year and day are present and month is missing:

If year = year of first dose, then set month to month of first dose.

If year < year of first dose, then set month to December.

If year > year of first dose, then set month to January.

If month and year are present and day is missing:

If year = year of first dose and

if month = month of first dose, then set day to day of first dose

if month < month of first dose, then set day to last day of month

if month > month of first dose, then set day to first day of month

if year < year of first dose, then set day to last day of month

if year > year of first dose, then set day to first day of month

For all other cases, set onset date to date of first dose

Concomitant Medications

Start Date:

If start date is completely missing and end date is not before first dose, then the medication will be classified as both prior and concomitant. Else if start date is completely missing and end date is before first dose, then the medication will be classified as prior.

If (year is present and month and day are missing) or (year and day are present and month is missing), then set month and day to January 1.

If year and month are present and day is missing, then set day to first day of month.

End Date:

If end date is completely missing and start date is not after first dose, then the medication will be classified as both prior and concomitant. Else if end date is completely missing and start date is after first dose, then the medication will be classified as concomitant.

If (year is present and month and day are missing) or (year and day are present and month is missing), then set month and day to December 31.

If year and month are present and day is missing, then set day to last day of the month.

Note that if both start and end dates are missing, then the medication will be classified as prior and concomitant.

17. Appendix D: List of Tables, Listings, and Figures

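### SAP Appendix C: when only the month of an AE onset is missing, the imputed date can fall before first dose and remove an on-treatment event from the TEAE tables

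*SAP*

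**What the plan says.** The adverse event part of SAP Appendix C has a branch that opens "If year and day are present and month is missing". Its same-year rule is "If year = year of first dose, then set month to month of first dose". For a later year it is "If year > year of first dose, then set month to January". For an earlier year the month becomes December. The recorded day is kept throughout.

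Two neighbouring same-year rules deal with onsets whose position relative to first dose is equally unknown:

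- Month and day both missing: "If year = year of first dose, then set month and day to month and day of first dose".
- Day missing, month known: "if month = month of first dose, then set day to day of first dose".

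A completely missing onset date, and any case not otherwise covered, also goes to the first-dose date.

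SAP 9.1 uses the imputed onset for three things: treatment emergence, the primary or booster period, and inclusion in summary tables. An AE is treatment-emergent if it starts on or after first dose, or if it is ongoing at first dose and then rises in CTCAE grade. Tables include TEAEs that start before last dose plus 28 days. SAP 9.1 adds: "Adverse events that begin prior to first dose will be captured in the medical history".

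SAP 9.1.1 promises listings of all AEs and SAEs, then says: "Adverse events presented in the listings will be those recorded from the first dose date through the end of follow-up". Protocol 9.7 promises by-subject listings of all AEs.

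**The concern.** Keeping the recorded day while borrowing the month of first dose gives a pre-dose date whenever that day is earlier in the month than the day of first dose. A record that carries more information (year and day) can then be treated less cautiously than one that carries the year alone, which goes to the first-dose date and stays in the tables.

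At stake is whether a real on-treatment event is counted in the tables of TEAEs, related TEAEs and serious TEAEs. This is a stated rule that can give a wrong classification. It is not a gap left for the programmer to fill.

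**Working it through.** The documents give no figure on this point, so there is none to reproduce.

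**Does the rule produce a pre-dose date?** Take first dose on 20 March and true onset on 5 June of the same year, with the month not recorded. Day 5 is kept and the month becomes March, so the imputed onset is 5 March, 15 days before first dose. The general fallback to the first-dose date does not apply, because this pattern has its own branch.

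**Inputs**

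- Vaccinations in Weeks 1, 3, 5, 9, 13, 17 and 21 (SAP 3.3). The last is 20 × 7 = 140 days after the first.
- Table window: 140 + 28 = 168 days (SAP 9.1).
- Assumptions, not in the documents: full course given, first dose uniform over a 365-day year, onset uniform over the window. Impossible dates such as 31 February (about 1.3% of same-year cases) go to the first-dose date under the general fallback.

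**Enumeration**

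- All pairs of first dose and onset: 365 × 168 = 61,320.
- Onset in the calendar year of first dose: 47,292 (77.1%). The other 22.9% go to January of the next year, which is after first dose.
- Imputed before first dose: 20,745.
- Share of same-year events: 20,745 / 47,292 = 43.9%.
- Share of all missing-month on-treatment events: 20,745 / 61,320 = 33.8%.

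**Sensitivity, same-year events**

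| Assumption | Imputed before first dose |
|---|---|
| Uniform onset, windows of 28 to 197 days | 42.3% to 44.2% |
| Onset clustered in the 1 to 7 days from each injection | 52% to 56% |
| Front-loaded exponential onset, mean 14 / 28 / 56 days | 30% / 37% / 41% |
| Uniform onset, first dose on the 1st / 10th / 15th / 20th / 31st | 0% / 25% / 40% / 57% / 98% |

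**Opposite direction.** AE collection starts at consent (Protocol 8.4 and 8.12), and screening can run for the 28 days before dosing (Protocol 7.1). With first dose on 5 March and true onset on 20 February, the imputed onset is 20 March, which is treatment-emergent. For onsets uniform over those 28 days (an assumption), 9,814 of 365 × 28 = 10,220 pairs are in the same year. Of these, 4,466 are imputed on or after first dose: 4,466 / 9,814 = 45.5%.

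**Effect of a floor at first dose.** The 43.9% falls to 0%. Of the 20,745 pairs it moves, 19,744 (95%) have a true onset 14 or more days after first dose, that is, from the scheduled Week 3 booster onward. The floor places them on the first-dose date, in the primary period.

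**The case against.** The strongest reply is that this is a narrow drafting gap from which a reader could infer too much. Four stronger readings are tempting, and the documents support none of them.

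- **The events also vanish from the AE listings.** SAP 9.1 names emergence, period and summary tables as the uses of imputed dates, not listings. SAP 9.1.1 and Protocol 9.7 both promise listings of all AEs. The sentence limiting listings to events recorded from first dose does not say that an imputed onset decides inclusion. The medical-history sentence says where pre-dose events are captured, not that an AE record moves because its date was imputed. The listing rule is unclear, but loss is not established.
- **The error only ever removes events.** The branch also makes some pre-dose events treatment-emergent.
- **44% is a property of the plan.** It is conditional on the calendar year and on assumed onset and first-dose distributions.
- **An SAE could be lost altogether.** SAEs are reported within 24 hours (Protocol 8.13 and 8.14) and eCRFs are due within 5 days of a visit (Protocol 11.3). A serious event with an unknown month is therefore unlikely, and it would still be in the SAE reports. Only its count in the summary tables is exposed.

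The medication rule for the same pattern ("year and day are present and month is missing), then set month and day to January 1" for start dates) is no precedent for a floor either. It serves prior or concomitant classification, and 1 January will itself usually precede first dose.

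All of this limits the point without removing it. The branch has no floor, the fallback does not reach it, and its neighbours with unknown timing behave differently.

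**Conclusion.** The point holds as a minor defect in one imputation branch. A true on-treatment AE in the first-dose year, with day known and month missing, can be dated before first dose and drop out of the TEAE tables unless the grade-worsening route keeps it in.

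The share misdated is about 44% of same-year events with this pattern under uniform assumptions, 30% to 56% under the other onset patterns tried, and about 34% of all missing-month on-treatment events. These are shares of a pattern that is probably rare and whose frequency the documents do not give, so the absolute number is likely small. Misclassification runs both ways.

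**What to change.** Add to this branch of Appendix C: if the resulting date is before the date of first dose, set onset to the date of first dose, unless a recorded end date is before first dose. In SAP 9.1.1, state that AE listings include all AEs regardless of imputed onset, and align the sentence that limits listings to events from first dose.

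The cost is one clause, one clarifying sentence and a line of code. There are two downsides:

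- Same-year pre-dose events with this pattern will count as treatment-emergent unless their end date shows otherwise. These should be few.
- Most of the rescued events will be booster-period events counted in the primary period, so the overall TEAE tables improve more than the by-period tables do.

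The neighbouring branches that default to the first-dose date already accept both.
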